5.1.2. Secondary Efficacy Variables

Secondary efficacy variables include OS and ORR (CR and PR).

5.1.2.1. Overall Survival (OS)

OS is defined as the time from the date of randomization to death due to any cause. Subjects who are alive at the time of data cut off for OS analysis will be censored at the last contact date at which the subject is known to be alive.

Survival status data will be obtained from deaths reported in the CRFs and Survival follow-up communications every 3 months after a subject discontinues from study treatment.

The last contact date is defined as the last date the subject was known to be alive at the analysis cut-off. The date will be the latest date among the following:

- Last non-missing assessment/onset date captured under the following eCRF pages (or if a date of assessment/onset is not available the “date of visit” for the eCRF page can be used): adverse events, vital signs, physical examination, ECOG PS, ECG, Echocardiogram or MUGA scan, safety laboratory test, tumor assessment, patient-reported outcomes assessment, hospitalization and also assessment date in third-party data such as PK, HAHA etc.
- Last dosing date of study medication, last date of concomitant medications, and last date of non-drug treatments/procedures.
- Start date of subsequent anti-cancer therapy administered after study treatment discontinuation.
- Date of Last Contact collected on the survival follow up page of the eCRF.

- Date of Last Contact collected on the final subject status (or end of study status) page of the eCRF.

5.1.2.2. Object Response Rate (ORR)

ORR is defined as the proportion of subjects with the best overall response of CR or PR. A confirmation of CR/PR is not required for this study as per RECIST Version 1.1.

The best overall response is defined as the best response (in the order of CR, PR, SD, and PD) among all overall responses recorded from the start of treatment until the subject is withdrawn from the study. The best overall response of PD corresponds to disease progression (assessment based upon tumor measurements and recorded on the CRF page “overall tumor assessment”) for the first valid post-treatment tumor assessment. If there is no post-treatment tumor assessment, the best overall response will be assigned as “Inevaluable”. In the case of a best overall response of SD, measurements must have met the SD criteria at least once after study entry at a minimum time interval from baseline. A best overall response of SD must be assessed a minimum of 39 days (6 weeks – 3 day visit window) after the date of randomization. If this minimum requirement is not met, the best overall response will be determined starting with the next tumor assessment. If there is no next tumor assessment, the best overall response will be assigned as “Inevaluable”.

5.1.3. Exploratory Efficacy Variables

Duration of response, time to response, time to disease progression and duration of SD will be exploratory efficacy variables examined in this study.

5.1.3.1. Duration of Response

Duration of response is defined as the time from the date of the first documentation of objective response (CR or PR) to the date of the first documentation of progressive disease (disease progression as assessed based upon tumor measurements and recorded on the CRF page “overall tumor assessment”). If a subject is discontinued or is lost to follow-up with no documentation of progressive disease, duration of response is defined as the time from the date of the first documentation of objective response to the date of the last evaluable tumor assessment as a censored value. The rules for censored cases are defined as follows:

Subjects who progress after ≥ 2 consecutive missed tumor assessment visits will be censored at the date of the last evaluable tumor assessment prior to the tumor assessment of progressive disease. In this study, progression after ≥ 2 consecutive missed tumor assessment visits is defined as progression that occurs more than 13 weeks (two tumor assessment visits plus 1 week visit window) since the last post-baseline evaluable tumor assessment. Subjects who start other anti-cancer therapy prior to progression will be censored at the date of the last post-baseline evaluable tumor assessment prior to starting other anti-cancer therapy.

Duration of response will be measured for responding subjects (PR or CR) only.

5.1.3.2. Time to Response

Time to response is defined as the time from the date of randomization to the date of the first documentation of objective response (CR or PR). Time to response will be measured for responding subjects (PR or CR) only.

5.1.3.3. Time to Disease Progression (TTP)

Time to progression is defined as the time from the randomization date to the date of first objective documentation of radiographic disease progression (per RECIST v1.1 as assessed by investigator). Objective documentation of disease progression is based upon "Overall Response" recorded as "Progressive Disease (PD)" on the CRF page: "overall tumor assessment". The rules for censored cases of TTP and duration of response are similar to the censoring of PFS, except that subjects who die before disease progression is documented are censored for the former.

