#### **4.1.4. Reasons for Discontinuation of Study Treatment**

Reasons for discontinuation of a subject from the study include: PD as per RECIST 1.1 or clinician's assessment, AE, death, withdrawal of consent by subject, significant protocol violation, or sponsor decision to terminate the study.

In the event of a decision to discontinue study drug treatment the investigator will contact the subject directly to explain the circumstances requiring study treatment to be stopped. The subject will be instructed to attend the safety follow-up visit required by the study protocol, and the treating physician will discuss alternative treatment options with the subject.

The reason for discontinuation will be recorded.

Subjects may be withdrawn from the study after signing informed consent for the following reasons:

- Adverse Event
- Lost to Follow-up
- Withdrawal of Consent by Subject
- Physician Decision
- Death
- Pregnancy
- Progressive Disease

- Study Terminated by Sponsor
- Other

All subjects who are withdrawn from the study should complete protocol specified withdrawal procedures, unless they withdraw their consent (Section 4.1.5).

Elevations in AST/ALT and/or total bilirubin that meet the criteria described in Table 4.1 require permanent discontinuation of the subject from patritumab/placebo and cetuximab.

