5.1.3.4. Duration of Stable Disease (SD)

Duration of stable disease is defined for subjects whose best response is SD as the time from the date of randomization to the date of the first documentation of progressive disease (disease progression as assessed based upon tumor measurements and recorded on the CRF page "overall tumor assessment"). Censoring rules are the same as described above for duration of response.

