8.2.3.3. Time to Disease Progression

Median time to disease progression will be estimated along with two-sided 80% and 95% CIs using Kaplan-Meier methods by treatment. In addition, summary statistics for 25% and 75% percentiles will be estimated using Kaplan-Meier methods.

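### Duration of response and duration of stable disease censor deaths without progression, so their Kaplan-Meier summaries run long whenever such deaths occur

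*SAP*

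**What the plan says.** - **Duration of response (SAP 5.1.3.1).** It runs from first response "to the date of the first documentation of progressive disease". Death is not in the event definition. The censoring rule begins "If a subject is discontinued or is lost to follow-up with no documentation of progressive disease" and censors at the last evaluable tumor assessment. Death is one of the listed reasons for discontinuation (Protocol 4.1.4: "AE, death, withdrawal of consent by subject"), so a responder who dies without progression falls under that rule.
- **Duration of stable disease (SAP 5.1.3.4).** It runs from randomization to documented progression. "Censoring rules are the same as described above for duration of response".
- **Time to progression (SAP 5.1.3.3).** Its censoring, together with that of duration of response, is said to resemble the PFS rules, with one departure: "except that subjects who die before disease progression is documented are censored for the former".
- **Reporting.** SAP 8.2.3.1 plans a Kaplan-Meier plot and quartiles for duration of response. SAP 8.2.3.4 plans the same for duration of stable disease, plus a median with 80% and 95% intervals. For time to progression, SAP 8.2.3.3 states: "Median time to disease progression will be estimated along with two-sided 80% and 95% CIs using Kaplan-Meier methods by treatment". The shell of Table 15.2.4 counts only radiographic progression as the event for both durations and gives medians and quartiles.
- **Status.** SAP 5.1.3 lists all of these as exploratory. PFS (SAP 5.1.1) counts death from any cause as an event, subject to its censoring rules.

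**The concern.** Kaplan-Meier censoring assumes that a censored subject could still have the event later, at the same rate as those who remain under observation. That cannot hold for someone who has died. For a duration of benefit, the death ends the benefit; censoring it redistributes the subject's weight to those still in response or still stable, and the curve moves to the right.

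Two features of the plan make such deaths plausible. Clinical deterioration without radiographic evidence is not a progression event (SAP 5.1.1), so a subject who declines and dies before a scan has no event in these endpoints. After week 24 the scans are 12 weeks apart (SAP 5.1), which widens the interval in which death can come before documentation.

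The sensitivity analyses in SAP 8.2.4.1 cover clinical progression as a PFS event and a changed HRG cutoff. Neither counts death in the two durations. A reader of Table 15.2.4 would see medians that are too long, with nothing to indicate it.

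**Working it through.** **The plan's own figure.** The documents give no number for these durations. The nearest stated figure is 53 PFS events (SAP 4: hazard ratio 0.56, one-sided alpha 0.10, 80% power, 1:1). The Schoenfeld formula gives 4 × (1.2816 + 0.8416)² / (ln 0.56)² = 18.03 / 0.3362 = 53.6, and power at 53 events is 79.6%. The figure is reproduced. It does not depend on how the durations are defined.

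**Inputs for the bias.**
- f: share of first events that are deaths without documented progression. Not in the documents; assumed 10%, 20%, 30%.
- m: median with death counted as an event. The planning medians for PFS, 4.2 and 7.5 months (SAP 4), serve only as illustrative values.

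**Formula.** Take constant hazards: λ(1−f) for progression and λf for death, with λ = ln 2 / m. With death as an event, the curve is exp(−λt) and its median is m. With death censored, the Kaplan-Meier curve estimates exp(−λ(1−f)t), whose median is m/(1−f).

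| f | 1/(1−f) | m = 4.2 becomes | m = 7.5 becomes |
|---|---|---|---|
| 10% | 1.11 | 4.67 | 8.33 |
| 20% | 1.25 | 5.25 | 9.38 |
| 30% | 1.43 | 6.00 | 10.71 |

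**With the planned scans.** A simulation used m = 4.2, 300 runs of 200 subjects, scans every 6 weeks to week 24 and then every 12 weeks, deaths without recorded progression censored at the last scan, and no other censoring. The medians (death as event against death censored) were 4.8 against 5.5 months at f = 10%, 4.7 against 6.3 at 20% and 4.6 against 7.6 at 30%. The gap exceeds 1/(1−f) because some subjects who have progressed die before the scan that would record it, and because censoring is moved back to the last scan. The simulated clock starts at time zero with no selection on best response, so it is a rough guide only.

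**Against sampling error.** Assume 14 responders in an arm and a true median duration of 5.6 months (neither is in the documents), with no other censoring. The standard error of the median is about 1/(λ√n), with λ = 0.693/5.6 = 0.1238 and √14 = 3.742, so 1/0.463 = 2.16 months. The shifts are 5.6/0.9 − 5.6 = 0.62, 5.6/0.8 − 5.6 = 1.40 and 5.6/0.7 − 5.6 = 2.40 months, or about 0.3, 0.6 and 1.1 standard errors.

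**Between arms.** The ratio of medians is multiplied by (1−f_control)/(1−f_patritumab). At 20% in both arms, 9.375/5.25 = 1.79, the same as 7.5/4.2 = 1.79. With equal true medians and shares of 30% (patritumab) and 10% (control), the spurious ratio is 0.9/0.7 = 1.29.

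**The case against.** The best case for the plan is that these are deliberate progression-only endpoints. PFS supplies the death-inclusive measure and OS the mortality measure. The endpoints are exploratory, and SAP 8.2.3 plans no test, hazard ratio or difference for them. Responders and stable-disease subjects are subsets formed after randomization, so they are not a randomized comparison in any case. The size rests wholly on assumed death shares and, for responders, is around one standard error or less.

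Most of this stands and limits the point. It does not remove it: a duration of benefit that ignores death is too long for any share above zero, and the plan contains no version that shows this.

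Four stronger readings are tempting and are not supported:

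- *That time to progression is wrongly defined.* Censoring death is what conventionally separates it from PFS. The error would lie in reading one minus Kaplan-Meier as the proportion progressed. With m = 4.2 and f = 30%, that gives 75% at 12 months against a cumulative incidence of 60%. But neither SAP 8.2.3.3 nor Table 15.2.4 plans a 12-month rate for this endpoint.
- *That the arm comparison is biased whenever hazards differ.* Equal death shares leave the ratio of medians unchanged, and nothing in the documents suggests unequal shares.
- *That PFS counts every one of these deaths.* SAP 5.1.1 censors deaths after new anti-cancer therapy and deaths more than 13 weeks after the last evaluable assessment.
- *That the wording in SAP 5.1.3.3 leaves duration of response untouched.* The phrase about the former could be read as time to progression alone, but the event definition in SAP 5.1.3.1 and the shell of Table 15.2.4 lead to the same result.

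**Conclusion.** The point holds for duration of response and duration of stable disease, as a minor one. The direction is certain wherever a death without documented progression occurs. The size is not known: about 11%, 25% and 43% on the median at assumed death shares of 10%, 20% and 30% under constant hazards, and somewhat more in the simulation with the planned scans. A distorted ratio between arms needs a death share that differs by arm. A reader might infer that the efficacy conclusion is at risk. It is not: the primary PFS test, its alpha and the 53-event requirement do not use these endpoints.

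**What to change.** 1. In SAP 5.1.3.1 and 5.1.3.4, define the event as first documented progression or death from any cause, with the PFS censoring rules of SAP 5.1.1. State that those rules still censor deaths after new anti-cancer therapy and deaths more than 13 weeks after the last evaluable assessment. The progression-only version can stay as a supplementary analysis.
2. Align the event rows and notes of Table 15.2.4, and the matching notes of Listing 16.2.6.3.
3. Reword SAP 5.1.3.3 to name the endpoints to which the death exception applies. Time to progression can keep its definition. Optionally add the cumulative incidence of progression (Aalen-Johansen) with death as a competing event. Its ceiling is 1−f, so at f = 30% it levels off at 70% and the 75th percentile planned in SAP 8.2.3.3 could not be estimated.
4. In the same edit, correct SAP 8.2.3.1, which names the median time to response under duration of response, and the references in SAP 8.2.3.1, 8.2.3.2 and 8.2.3.4 to Sections 5.1.4.x; the definitions are in 5.1.3.x.

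The cost is SAP wording, shell edits and a little programming. Death dates are already collected for OS, and Protocol 11.4.3 leaves these definitions to the SAP, so no new data are needed. Reported durations become somewhat shorter.

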5.1.3.4. Duration of Stable Disease (SD)

Duration of stable disease is defined for subjects whose best response is SD as the time from the date of randomization to the date of the first documentation of progressive disease (disease progression as assessed based upon tumor measurements and recorded on the CRF page "overall tumor assessment"). Censoring rules are the same as described above for duration of response.

5.2. Safety Variables

5.2.1. Adverse Events

The following safety variables will be assessed in this study according to the Schedule of Events (Table 3.1.1 and Table 3.1.2) in Section 3.1.

- A Treatment-emergent adverse event (TEAE) is defined as an Adverse Event (AE) that emerges during treatment, having been absent at pretreatment, or reemerges during treatment, having been present at baseline but stopped prior to treatment, or worsens in severity since treatment relative to the pretreatment state, when the AE is continuous. Adverse events will be coded using the Medical Dictionary for Regulatory Activities (MedDRA, Version XX.X), and graded according to the National Cancer Institute (NCI) Common Terminology Criteria for Adverse Events (CTCAE) Version 4.03.
- AEs of Special Interest
 - Interstitial Lung Disease (ILD)
ILD is defined as an acute onset of new or progressive pulmonary symptoms, such as dyspnea, cough or fever.
 - Combined Elevations of Aminotransferases and Bilirubin
Hepatic events, both serious and nonserious, presenting with combined abnormalities meeting criteria for a potential "Hy's law" case [i.e., Alanine

aminotransferase (ALT) or Aspartate aminotransferase (AST) $\geq 3 \times$ ULN, with simultaneous total bilirubin $\geq 2 \times$ ULN].

5.2.2. Clinical Laboratory Evaluations

Safety laboratory assessments will include hematology, serum chemistry, coagulation, and urinalysis.

- Coagulation (only at Screening): prothrombin time, international normalized ratio, and partial thromboplastin time
- Hematology: CBC including hemoglobin, hematocrit, white blood cell count (WBC) with 5 part differential (including absolute neutrophil count), red blood cell, and platelet count
- Serum chemistry: bicarbonate, calcium, phosphorus, magnesium, albumin, glucose, serum creatinine, uric acid, total protein, urea, AST, ALT, lactic dehydrogenase, alkaline phosphatase, total and direct bilirubin, sodium, potassium, and chloride
- Routine urinalysis: dipstick and microscopy (if indicated), including protein, specific gravity, glucose, and blood
- Serum or urine β -HCG pregnancy test

At Screening, creatinine clearance (mL/min) or GFR will be calculated. This will also be done before each cisplatin or carboplatin administration.

5.2.3. Vital Signs

Vital sign measurements include blood pressure, heart rate, temperature, height, and weight.

5.2.4. ECG

A 12-lead ECG will be performed within 14 days prior to Screening, at the End of Study Treatment visit, and during the study at the discretion of the Investigator.

5.2.5. Physical Examinations

Physical examinations will evaluate the following body systems/organs: respiratory, cardiovascular, gastrointestinal, musculoskeletal, genitourinary/reproductive (optional), psychiatric (optional), hematological, neurological, immunological, head, eyes, ears, nose and throat, and other. Abnormal physical examination findings that are new or changed will be reported as AEs.

5.2.6. Other Safety Variables

An echocardiogram or multigated acquisition (MUGA) scan will be performed at screening, and at End-of-Study Treatment visit and during the study at the discretion of the Investigator.

The presence of anti-patritumab neutralizing antibody in serum will be assessed. Blood samples will be taken on Day 1 of Cycle 1 (preinfusion), Cycle 2 (preinfusion), Cycle 3 (preinfusion), and at End-of-Study Treatment visit. For subjects with positive anti-patritumab neutralizing antibody on the serum sample drawn at the end of study treatment visit, additional serum samples should be obtained for antibodies, until the antibody level returns to baseline (or becomes negative) or up to 1 year from the last dose of study drug or if the subject starts another therapy for cancer, whichever occurs first.

5.3. Pharmacokinetic Variables

5.3.1. Concentration Data

Serum concentrations for patritumab will be collected at Cycles 1- 3 and at End of Study Treatment (Table 8.1 of the Protocol).

For a subset of 30 subjects, a blood sample for PK analyses of patritumab, cetuximab, and platinum concentrations will be obtained at the time points, relative to the start of patritumab infusion at Cycle 1 (Table 8.2 of the Protocol). This will be an intense pharmacokinetic (PK) assessment.

5.3.2. Pharmacokinetic (PK) Parameters

PK parameters (AUC_{0-21d} and C_{max}) will be calculated from the individual concentrations of patritumab, cetuximab, cisplatin and carboplatin using non-compartmental methods. PK parameters will be derived for the intensive PK sampling (i.e. Cycle 1) for patritumab, cetuximab, cisplatin and carboplatin.

5.4. Pharmacodynamic (PD) Variables

Not Applicable.

5.5. Biomarkers

A predictive biomarker will be analyzed with the intent of identifying those subjects who might derive clinical benefit from treatment with patritumab. Heregulin is the candidate biomarker prospectively selected as the single predictive biomarker. Heregulin messenger RNA will be measured in tumor samples using a quantitative reverse transcription polymerase chain reaction assay.

HPV status or p16 will be evaluated in all tumor tissue in this study.

Further exploratory tissue, soluble, or genomic biomarkers in subject tissue and blood samples (possibly including circulating cell-free DNA and exosomes) may be analyzed based on emerging scientific knowledge to better understand the target disease and also the effects of study treatment.

5.6. Other Variables

5.6.1. Eastern Cooperative Oncology Group Performance Status

The Eastern Cooperative Oncology Group (ECOG) performance status will be determined at Screening, and then at each scheduled visit throughout the study.

5.6.2. Patient Reported Outcomes

Patient-reported outcomes will be used to evaluate study treatment in subjects treated with patritumab + cetuximab + platinum-based therapy compared to placebo + cetuximab + platinum-based therapy.

Functional Assessment of Cancer Therapy—Head and Neck (FACT-H&N) Instrument

The FACT-H&N contains 4 general subscales (total 27 items) measuring physical well-being (PWB), functional well-being (FWB), social well-being (SWB), emotional well-being (EWB), and a Head and Neck Cancer symptom-specific subscale – the 12-item Head and Neck Additional Concerns Subscale (HNS). Each of the 39 FACT-H&N items is rated on 5-point scales, ranging from 0=not at all to 4=very much, where higher scores represent more favorable patient-reported outcomes.

Combining the 10 symptom-related items out of the 39 FACT-H&N items – “I have a lack of energy” (PWB item 1), “I have nausea” (PWB item 2), “I have pain” (PWB item 4), “I worry that my condition will get worse” (EWB item 6), “I am content with the quality of my life right now” (FWB item 7), “I have trouble breathing” (Additional Concerns item 3), “I can swallow naturally and easily” (Additional Concerns item 7), “I am able to communicate with others” (Additional Concerns item 10), “I can eat solid foods” (Additional Concerns item 11), and “I have pain in my mouth, throat or neck” (Additional Concerns item 12) - yields a 10-item FACT-Head and Neck Symptom Index (FHNSI).

Specifically, 7 specific summary scores will be evaluated,

- PWB score
- FWB score
- SWB score
- EWB score
- HNS score
- FHNSI score
- FACT-H&N total score

The FACT-H&N Total Score ranges from 0-156. The PWB score, SWB score and EWB score range from 0 to 28. The EWB score ranges from 0 to 24. The HNS score and the FHNSI score ranges from 0 to 48. The FACT-H&N total score, PWB score, FWB score,

SWB score, EWB score, HNS score and FHNSI score will be analyzed as exploratory efficacy parameters.

Use following algorithm to determine the individual subscale scores:

- Physical well-being (PWB): PWB score = $\text{Sum (GP1-GP7)} \times 7 / \text{number of nonmissing items}$. If the number of missing items (GP1-GP7) is greater than 3, then set PWB score = missing.
- Social well-being (SWB): SWB score = $\text{Sum (GS1-GS7)} \times 7 / \text{number of nonmissing items}$. If the number of missing items (GS1-GS7) is greater than 3, then set SWB score = missing.
- Emotional well-being (EWB): EWB score = $\text{Sum (GE1-GE6)} \times 6 / \text{number of nonmissing items}$. If the number of missing items (GE1-GE6) is greater than 3, then set EWB score = missing.
- Functional well-being (FWB): FWB score = $\text{Sum (GF1-GF7)} \times 7 / \text{number of nonmissing items}$. If the number of missing items (GF1-GF7) is greater than 3, then set FWB score = missing.
- Additional Concern (HNS): HCS score = $\text{Sum (H\&N1-H\&N12)} \times 12 / \text{number of nonmissing items}$. If the number of missing above items is greater than 6, then set HCS score = missing.
- Additional Concern (HNS): HCS score = $\text{Sum (H\&N1-H\&N12)} \times 12 / \text{number of nonmissing items}$. If the number of missing above items is greater than 6, then set HCS score = missing.
- FHNSI: FHNSI score = $\text{Sum of 10 symptom-related items} \times 10 / \text{number of nonmissing items}$. If the number of missing above items is greater than 5, then set FHNSI score = missing.
- FACT-H&N total score: FACT-H&N score = $\text{Sum (PWB, SWB, EWB, GFB, HCS)}$. If any of the above items is missing, then set FACT-H&N score = missing.

EuroQoL-5 Dimensions-5 Levels Instrument

The EQ-5D-5L is a preference based measure of health status that is now widely used in clinical trials, observational studies, and other health surveys.

The EQ-5D-5L consists of 2 pages – the EQ-5D-5L descriptive system and the EuroQoL Visual Analogue scale (EQ VAS). The descriptive system comprises the following 5 domains: mobility, self-care, usual activities, pain/discomfort, anxiety/depression. Each domain has 5 levels: no problems (1), slight problems (2), moderate problems (3), severe problems (4), and extreme problems (5). The respondent is asked to indicate his/her health state by ticking (or placing a cross) in the box with the most appropriate statement in each of the 5 domains. This decision results in a 1-digit number expressing the level selected for that domain. The digits for 5 domains can be combined in a 5-digit number or profile describing the respondent's health state.

As index-based values have not been evaluated for the EQ-5D-5L at this time, crosswalk value sets developed based on the EQ-5D-3L index-based values will be applied. The crosswalk value set for the United Kingdom will be used for analyses overall and for all regions. The value set provides an index score for each health state and can be accessed at:

(http://www.euroqol.org/fileadmin/user_upload/Documenten/Excel/Crosswalk_5L/EQ-5D-5L_Crosswalk_Value_Sets.xls).

The EQ VAS records the respondent's self-rated health on a 20 cm vertical, visual analogue scale with endpoints labeled 'the best health you can imagine' and 'the worst health you can imagine'. This information is used as a quantitative measure of health as judged by the individual respondents. The instructions for the EQ VAS asks respondents to 'mark an X on the scale to indicate how your health is TODAY' and then to 'write the number you marked on the scale in the box below.'

Approved

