**FACT-H&N (Version 4)**

Please circle or mark one number per line to indicate your response as it applies to the past 7 days.

ADDITIONAL CONCERNS		Not at all	A little bit	Some- what	Quite a bit	Very much
H&N1	I am able to eat the foods that I like .....	0	1	2	3	4
H&N2	My mouth is dry .....	0	1	2	3	4
H&N3	I have trouble breathing .....	0	1	2	3	4
H&N4	My voice has its usual quality and strength .....	0	1	2	3	4
H&N5	I am able to eat as much food as I want .....	0	1	2	3	4
H&N6	I am unhappy with how my face and neck look.....	0	1	2	3	4
H&N7	I can swallow naturally and easily .....	0	1	2	3	4
H&N8	I smoke cigarettes or other tobacco products .....	0	1	2	3	4
H&N9	I drink alcohol (e.g. beer, wine, etc.).....	0	1	2	3	4
H&N 10	I am able to communicate with others .....	0	1	2	3	4
H&N 11	I can eat solid foods.....	0	1	2	3	4
H&N 12	I have pain in my mouth, throat or neck .....	0	1	2	3	4

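### FACT-H&N scoring in SAP 5.6.2 reverses no item and excludes none: smoking and alcohol count in a head and neck symptom score, and worse symptoms raise scores the SAP calls better when higher

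*SAP*

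**What the plan says.** SAP 5.6.2 presents HNS as the subscale specific to head and neck cancer symptoms, "the 12-item Head and Neck Additional Concerns Subscale (HNS"). It describes the 39 FACT-H&N items as rated on a scale "ranging from 0=not at all to 4=very much, where higher scores represent more favorable patient-reported outcomes". Protocol 10.2.1 agrees: the twelve items are there to assess head and neck symptoms, and higher means better quality of life.

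The scoring rule in SAP 5.6.2 adds H&N1 to H&N12, multiplies by 12 and divides by the number of items answered. On missing items it says: "If the number of missing above items is greater than 6, then set HCS score = missing". The other subscales and the FHNSI are built in the same way, and the total is the sum of the five subscales. For ranges, the SAP states "The HNS score and the FHNSI score ranges from 0 to 48" and "The FACT-H&N Total Score ranges from 0-156".

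The questionnaire in Protocol 17.2.1 shows that H&N8 reads "I smoke cigarettes or other tobacco products" and H&N9 begins "I drink alcohol". Both are answered from 0 (not at all) to 4 (very much). Neither document reverses or leaves out any item. The item listing shell (Listing 16.2.9.1.1) has columns for raw and imputed scores only.

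**The concern.** Two separate faults sit in one scoring rule.

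- **Content.** Smoking and drinking are behaviours. They do not measure head and neck symptoms in either direction, yet they move a score described as symptom-specific, and the total with it. The SAP's own choice of ten symptom-related items for the FHNSI uses neither.
- **Direction.** Many items are worded so that agreement is bad. Summed without reversal, they push the score up as the patient gets worse, which contradicts the SAP's statement that higher is more favourable.

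The affected scores are used in several places. The total, the well-being subscales and the FHNSI go into the mixed model in SAP 8.7.1. HNS appears in the shells for Tables 15.5.1.1 and 15.5.1.2 and Figure 15.5.1.1. The baseline FACT-H&N total, split at its median, defines a subgroup for PFS and OS in SAP 8.2.4.2.

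**Working it through.** **Inputs.** Item counts are PWB 7, SWB 7, EWB 6, FWB 7, HNS 12 and FHNSI 10, each item scored 0 to 4 (SAP 5.6.2). Item wording comes from Protocol 17.2.1.

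**Stated ranges.** Maximum = number of items x 4.
- HNS: 12 x 4 = 48, as stated.
- Total: 28 + 28 + 24 + 28 + 48 = 156, as stated.
- FHNSI: 10 x 4 = 40, not the stated 48.

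The maxima of 48 and 156 are reached only if H&N8 and H&N9 are counted, so their inclusion is part of the plan.

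**Weight of the two habit items.** 2 x 4 = 8 points. That is 8/48 = 16.7% of the HNS range and 8/156 = 5.1% of the total range.

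**Effect under the SAP rule.** Hold the other ten HNS items and the 27 general items at 2 (27 x 2 = 54).

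| H&N8, H&N9 | HNS as written | Total as written | HNS if negative items reversed | Ten-item HNS |
|---|---|---|---|---|
| 0, 0 | 20 | 74 | 28 | 20 |
| 4, 0 or 0, 4 | 24 | 78 | 24 | 20 |
| 4, 4 | 28 | 82 | 20 | 20 |

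Going from none to the top response on both items adds 8 points as written. It removes 8 if H&N2, 3, 6, 8, 9 and 12 are reversed. Leaving the two items out gives no change.

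**Proration.** The rule allows six missing items. With four other items answered at 2, HNS is 8 x 12/6 = 16 when both habits are 0, and 16 x 12/6 = 32 when both are 4. The swing doubles to 16 points.

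**Reach of the missing reversal, habit items aside.**
- PWB: all 7 items are negatively worded, 7 x 4 = 28 of 28 points.
- EWB: 5 of 6 (all but the item on coping), 5 x 4 = 20 of 24.
- HNS: H&N2, 3, 6 and 12, 4 x 4 = 16 of 48.
- SWB and FWB: none.
- Total: 28 + 20 + 16 = 64 of 156 points (41%).
- FHNSI: energy, nausea, pain, worry, trouble breathing and mouth or throat pain, 6 x 4 = 24 of 40 points (60%).

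For PWB, the as-written score equals 28 minus the reversed score, so any difference between arms keeps its size and changes sign. The other affected scores mix the two directions.

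**Ranges after correction.** HNS 10 x 4 = 40; total 28 x 3 + 24 + 40 = 148; FHNSI 40.

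**The case against.** The strongest reply is that the SAP must intend reversal, because its statement that higher is more favourable can be true only if negative items are reversed, and the programmer will follow the cited manual. That may well happen. It is not what the algorithm says, however, and the SAP gives that algorithm as the instruction for computing the scores. The reply does settle one thing. A reader might infer that heavier smoking or drinking improves the score by the nature of these items. The documents do not support that: the upward direction comes from the missing reversal, and with reversal the same change lowers HNS by 8.

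Other points that stand:
- The FHNSI contains neither habit item, and Protocol 2.1.3 and SAP 2.3 name it for evaluating head and neck symptoms. The symptom objective keeps one measure free of the content fault, though not of the direction fault.
- SAP 8.7.1 does not list HNS by name among the modelled scores. It enters through the total and the table and figure shells.
- The 8 points are one subject's extreme change. In a randomised, blinded comparison of change from baseline, stable habits largely cancel.
- The FHNSI range is a text error. The formula already prorates to ten items, so no computed score exceeds 40.
- Protocol 10.2.1 itself defines HNS as twelve items. The documents show a mismatch of content but do not establish a ten-item rule, and the manual is not available here.

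**Conclusion.** The scoring in SAP 5.6.2 is wrong as written, measured against its own description. Two habit items carry up to 8 of 48 HNS points and 8 of 156 total points in a score said to be symptom-specific. The lack of any reversal makes worse symptoms raise PWB, EWB, HNS, FHNSI and the total. The direction fault is the larger of the two, and removing the habit items alone would leave it in place.

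The size rests on the algorithm being followed literally, and the 8-point figure on complete data. Two stronger inferences are not supported. The documents show no between-arm bias, since nothing indicates that habits would change differently by arm. The main efficacy results are not at risk either: SAP 5.6.2 and Protocol 11.7.1 treat these scores as exploratory, and the primary PFS test does not use them. The only contact with PFS and OS is the exploratory subgroup split on baseline total. The matter should be corrected, but it does not threaten the trial's main conclusion.

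**What to change.** Amend SAP 5.6.2 before unblinding:

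1. Reverse-score (4 minus the response) every negatively worded item before summing, listing the items by number for PWB, EWB, HNS and FHNSI.
2. Compute HNS from H&N1-7 and H&N10-12 as sum x 10/number of non-missing items, set to missing if more than 5 are missing (the rule already used for the ten-item FHNSI). Report H&N8 and H&N9 as single items.
3. Restate the ranges: HNS 0-40, FACT-H&N total 0-148, FHNSI 0-40.
4. Confirm the item list and the reversals against the scoring manual in the SAP's reference list, and record the result.

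The cost is SAP wording and scoring code, with no new data. The table shells already provide for individual HNS item scores. The downside is that two items move from the scale to single-item summaries. Fixing the rule while the data are still blinded avoids a scoring choice made after the results are known.
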